Outcome measures obtained after using the Revo-M foot for 8 weeks will be compared to baseline measures obtained using everyday feet with a 2-sided Wilcoxon matched pairs signed ranks test. The Hochberg method will be used to adjust alpha for the multiple primary effectiveness endpoints, thereby limiting the family-wise alpha to 0.05. In this method, p-values are ranked from highest to lowest for each primary endpoint tested. If the highest p-value is ≤ 0.05 , all null hypotheses will be rejected and no further adjustment will be made. If, however, the highest p-value is > 0.05 , alpha will be adjusted to 0.025 (alpha/2). The remaining p-value must be ≤ 0.025 in order to be statistically significant. Adjustment of alpha will continue in this manner for all primary effectiveness endpoints. Two-tailed p-values \leq the Hochberg adjusted alpha will indicate statistical significance. Primary efficacy endpoints (2 endpoints) will be considered one family and secondary efficacy endpoints (3 endpoints) will be considered a second separate family. The Hochberg method will not be applied to exploratory endpoints.

If the observed p-value is \leq the Hochberg adjusted critical value, the difference will be regarded as statistically significant. Because this is a randomized crossover study, the Revo-M may be either the first or second new foot used after baseline measures with the everyday feet. It is important to assess whether differences between Revo-M and everyday feet scores are influenced by the order in which the new feet are assigned. To evaluate this a difference score will be computed by subtracting everyday feet scores from Revo-M scores. Difference scores for subjects receiving the Revo-M foot first will be compared to those of subjects who received the Revo-M foot second (after a comparative foot) using Wilcoxon's rank sum test. A resulting p-value ≤ 0.05 will indicate that differences in the specified outcome measure may depend on the order in which the Revo-M was

assigned and not simply due to the Revo-M itself. Interpretation of differences between Revo-M and everyday feet scores will be modified accordingly.

Primary Efficacy Endpoints

Primary Efficacy Endpoint #1: Perception of mobility as measured by the PLUS-M. It is hypothesized that PLUS-M scores will be higher for subjects when they are using the Revo-M compared to their everyday feet. In statistical terms the null and alternative hypotheses are as follows:

$$H_0: \mu_{\text{Revo-M}} \leq \mu_{\text{Everyday}}$$

$$H_A: \mu_{\text{Revo-M}} > \mu_{\text{Everyday}}$$

Where H_0 is the null hypothesis, $\mu_{\text{Revo-M}}$ is the mean PLUS-M score using the Revo-M, μ_{Everyday} is the mean PLUS-M score using the everyday feet and H_A is the alternative hypothesis indicating that perception of mobility as measured by the PLUS-M is greater for Revo-M than for everyday feet.

The hypothesis will be tested using a 2-sided Wilcoxon matched pairs signed ranks test. If the observed p-value is \leq the Hochberg adjusted critical value and the mean of PLUS-M scores using the Revo-M foot is greater than PLUS-M scores using the everyday feet, the null hypothesis will be rejected in favor of the alternative hypothesis and the superiority of the Revo-M will be supported.

Primary Efficacy Endpoint #2: Level of activity restrictions as measured by the Trinity Amputation and Prosthesis Experience Scales Activity Restrictions subscale (TAPES-AR). It is hypothesized that TAPES-AR scores will be lower for subjects when they are using the Revo-M compared to their everyday feet. In statistical terms the null and alternative hypotheses are as follows:

$$H_0: \mu_{\text{Revo-M}} \geq \mu_{\text{Everyday}}$$

$$H_A: \mu_{\text{Revo-M}} < \mu_{\text{Everyday}}$$

Where H_0 is the null hypothesis, $\mu_{\text{Revo-M}}$ is the mean TAPES-AR score using the Revo-M, μ_{Everyday} is the mean TAPES-AR score using the everyday feet and H_A is the alternative hypothesis indicating that level of activity restrictions as measured by the TAPES-AR is less for Revo-M than for everyday feet.

The hypothesis will be tested using a 2-sided Wilcoxon matched pairs signed ranks test. If the observed p-value is \leq the Hochberg adjusted critical value and the mean of TAPES-AR scores using the Revo-M foot is less than TAPES-AR scores using the everyday feet, the null hypothesis will be rejected in favor of the alternative hypothesis and the superiority of the Revo-M will be supported.

Secondary Efficacy Endpoints

Secondary Efficacy Endpoint #1: Level of walking endurance as measured by the distance walked in the six-minute walk test (6MWT) and the perceived exertion (RPE) measured by Borg CR100. No hypothesis will be tested. Instead, the percentage of subjects (along with the exact 95% binomial confidence interval) with either a clinically meaningful improvement in the distance walked in the six minute walk test or a clinically meaningful decrease in the rating of perceived exertion (RPE) while wearing the Revo-M foot compared to the everyday foot will be computed. A clinically-significant improvement in the 6MWT is defined as a change in distance of greater than 45 meters [Resnik 2011]. A clinically-significant improvement in the RPE is defined as a change greater than 10 points [Ries 2005].

Secondary Efficacy Endpoint #2: Perception of balance confidence as measured by the extended Activities-specific Balance Confidence (ABC) Scale. It is hypothesized that ABC scores will be higher for subjects when they are using the Revo-M compared to their everyday feet. In statistical terms the null and alternative hypotheses are as follows:

$$H_0: \mu_{\text{Revo-M}} \leq \mu_{\text{Everyday}}$$

$$H_A: \mu_{\text{Revo-M}} > \mu_{\text{Everyday}}$$

Where H_0 is the null hypothesis, $\mu_{\text{Revo-M}}$ is the mean ABC score using the Revo-M, μ_{Everyday} is the mean ABC score using the everyday feet and H_A is the alternative hypothesis indicating that balance confidence as measured by the ABC scale is greater for Revo-M than for everyday feet.

The hypothesis will be tested using a 2-sided Wilcoxon matched pairs signed ranks test. If the observed p-value is \leq the Hochberg adjusted critical value and the mean of PLUS-M scores using the Revo-M foot is greater than PLUS-M scores using the everyday feet, the null hypothesis will be rejected in favor of the alternative hypothesis and the superiority of the Revo-M will be supported.

Secondary Efficacy Endpoint #3: Level of functional satisfaction as measured by the TAPES Functional Satisfaction (TAPES-FUN) subscale. It is hypothesized that TAPES-FUN scores will be higher for subjects when they are using the Revo-M compared to their everyday feet. In statistical terms the null and alternative hypotheses are as follows:

$$H_0: \mu_{\text{Revo-M}} \leq \mu_{\text{Everyday}}$$

$$H_A: \mu_{\text{Revo-M}} > \mu_{\text{Everyday}}$$

Where H_0 is the null hypothesis, $\mu_{\text{Revo-M}}$ is the mean TAPES-FUN score using the Revo-M, μ_{Everyday} is the mean TAPES-FUN score using the everyday feet and H_A is the alternative hypothesis indicating that level of functional satisfaction as measured by the TAPES-FUN subscale is greater for Revo-M than for everyday feet.

The hypothesis will be tested using a 2-sided Wilcoxon matched pairs signed ranks test. If the observed p-value is \leq the Hochberg adjusted critical value and the mean of TAPES-FUN scores using the Revo-M foot is greater than TAPES-FUN scores using the everyday feet, the null hypothesis will be rejected in favor of the alternative hypothesis and the superiority of the Revo-M will be supported.

Exploratory Efficacy Endpoints

Although hypotheses have not been specified, statistical testing will be done using Wilcoxon's matched pairs signed ranks test comparing Revo-M to both comparative devices, the Taleo and the ProFlex, and comparing the Revo-M to the everyday foot (baseline at the end of Period I and crossover at the end of Period IV). However, as these objectives are exploratory in nature, any statistically significant differences will be considered to be hypothesis generating and not definitive. These results may be used to guide future studies with prosthetic feet.

Time Period

Data collection for all subjects will be collected from the time of enrollment until the end of Period IV. Patients may be given the opportunity to continue in Phase V for continued follow-up with the Revo-M for an additional 6 months.

Data Analysis

Data analysis will be primarily descriptive in nature. Categorical variables (such as gender) and ordinal variables (such as severity of adverse events) will be summarized by absolute and relative (percentages) frequencies. Continuous variables (such as age) will be summarized by the mean, median, standard deviation, minimum and maximum values observed. In addition, change in continuous measures of effectiveness (such as PLUS-M scores) will be evaluated by subtracting baseline from follow-up scores. The mean, median, standard deviation, minimum and maximum values observed will be used to summarize change scores. In addition, the significance of differences between baseline and follow-up scores may be tested using Wilcoxon's matched pairs signed ranks test. Two-tailed p-values ≤ 0.05 will indicate statistical significance. Each variable will be analyzed separately. For each variable analyzed, only subjects with valid values will be included in the analysis. A subject need not have valid values on all variables to be included in the analysis of any given variable.

Risk-Benefit Analysis

The potential risks and benefits of the Revo-M as well as the comparative devices, Taleo and ProFlex XC, are identified in the Instructions for Use.

Risks and Minimization of Risks

The Revo-M devices to be assessed in this study will have undergone thorough verification testing. The risk analysis for the Revo-M prosthetic foot resulted in a list of known or expected risks as shown in the table below. All were deemed "As Low As Reasonably Possible."

Risk	Potential harm		
	Injury	Function lost	Health hazard
Damage/ Break of load bearing parts	X		
Break of functionally relevant parts	X		
Failure of the guide elements for the tension element	X	X	
The connection to the prosthesis is lost	X		
Foot twists	X		
Damage to the product during manufacture or use	X		
Incorrect alignment	X		
Not compliance with the assembly guidelines	X		
Mechanical damage	X		
Mechanical damage of load bearing parts	X	X	

Risk	Potential harm		
	Injury	Function lost	Health hazard
Use not according to the MOBIS classification	X		
Use without foot cover	X		
Overload of the prosthesis caused by unsuitable combination of prosthetic components	X		
Weight limit is not specified or not readable	X		
Safety instructions are not sufficiently described			X
Use on more than one user	X	X	
Product is used too long	X		
Exceeding the time-stability of supporting structures	X		

The following risk-minimizing measures will be taken:

- The subjects will be individually fit by an experienced CPO and instructed to report to the CPO all the problems with the prosthesis. The CPO will be trained by Ottobock in the handling of the new prosthetic foot.
- The first steps with the new prosthesis will be deliberately accompanied by exercises which accelerate adaptive behavior and train proper behavior in critical situations.
- The subjects will be instructed that in case of any technical issues concerning the prosthesis, they should stop using it until the issue is resolved and to contact the investigational site to schedule further steps.
- The participants will be informed that they should refrain from performing any activity if they do not feel confident or safe.
- All activities during in-clinic tests will be performed under the close supervision of qualified personnel.
- The Revo-M investigational device used in the study has passed a fatigue test for 750,000 gait cycles corresponding to approximately 9 months of use.

The risks to subjects inherent in study procedures are limited to those associated with the six-minute walk test. Complications associated with this test include excessive fatigue, angina, or light-headedness. Subjects' blood pressure and resting heart rate will be measured prior to the test in accordance with recommendations from the American Thoracic Society (ATS Statement, 2002). Subjects will be encouraged to stop during the test if needed to catch their breath, and the test may be stopped by the investigator if subjects exhibit symptoms listed above.

Benefits

Subjects may or may not experience benefits such as improved walking performance during the course of the study while wearing the study devices. In any case, all subjects will need to return the study devices at the end of the study and return to using their existing ESR feet. However, the study

results may help the Sponsor identify ways to improve future versions of the Revo-M. In addition, by characterizing the comparative safety and effectiveness of the Revo-M (relative to both existing ESR feet and the two comparative study feet), society, the O&P industry, and the Investigators may also benefit from the knowledge gained.

Study Management

Sponsor Responsibilities

Sponsor responsibilities include:

1. Ensuring the study is designed and managed in compliance with all appropriate regulatory standards and is conducted according to the Study Protocol.
2. Selecting Investigators qualified by training and experience to participate in the study.
3. Providing adequate training to Investigators, site research staff, and all Sponsor representatives.
4. Monitoring study data at investigational sites, including that proper informed consent is obtained prior to data collection and that patient confidentiality remains acceptable for the duration of the study.
5. Ensuring that prior to commencement of the study in each participating center, Sponsor has on file:
 - a. Written IRB approval
 - b. Signed Investigator's Agreement
 - c. Investigator's current curriculum vitae

Investigator Responsibilities

The Investigators will strictly follow requirements as stated in the Declaration of Helsinki and applicable local laws and regulations governing the conduct of clinical studies and subject data protection. They will be responsible for conducting the study as described in the Study Protocol and for the clinical well-being of the patients involved.

Records and Reports

The Investigator must retain all records and reports pertaining to this study. Electronic CRFs will be completed via Electronic Data Capture system by the Investigator. Completed originals of the source documents will be kept by the Investigator, if applicable. In addition, the following documents will be retained by the Investigator in each study site:

1. IRB correspondence, including approval letter, approved consent forms and annual or final reports if applicable
2. Sponsor correspondence
3. Source documents, signed data collection forms, medical records, office charts

4. Qualifications and evidence of training
5. Signed informed consent forms
6. Original Study Protocol and all revisions
7. Signed Study Agreement
8. Records concerning adverse events

All study documents will be retained by the Sponsor and Investigators for at least 2 years following the end of the study or earlier if approved by the Sponsor. No study documents will be destroyed or moved to a new location without prior written approval from the Sponsor. If the Investigator relocates, retires, or withdraws from the study for any reason, all records required to be maintained for the study should be transferred to an agreed-upon designee, such as another Investigator, or the institution where the study was conducted.

Investigator Reports

Table 5: Investigator Reports

Report	Submit To	Description
Unanticipated Adverse Device Effects	IRB, Sponsor	Notification within five working days after the investigator first learns of the event.
Withdrawal of IRB Approval	Sponsor	Notification within five working days

Sponsor Records

Sponsor will maintain the following records at a minimum:

- All significant correspondence which pertains to the investigation
- Signed Investigator agreements and curriculum vitae
- System/fitting related Adverse Device Effects and complaints
- All case report forms, including samples of patient informed consents, submitted by the Investigator and the Study Protocol
- Clinic staff training and study visit reports
- Sponsor will own and store the clinical data gathered in this study

Sponsor Reports

Table 6: Sponsor Reports

Report	Submit To	Description
Unanticipated Adverse Device Effects (US)	Investigators, IRB	Notification within five working days after the sponsor first learns of the event.
Withdrawal of IRB Approval	Investigators, IRB	Notification within five working days
Annual Report	Investigators	Report detailing the annual progress of the study.
Final Report	Investigators, IRB	Sponsor will notify the Investigator(s) within 30 working days of the completion or termination of the study. The Investigators will in turn inform their IRB. A final report will be submitted to the Investigator(s) after completion or termination of this study. The Investigator should confirm the receipt of the final report composed by Sponsor. The Investigator will also forward a copy of the report to their IRB.

Monitoring procedures

The study site is required to conduct the study in accordance with the Study Protocol, all applicable laws and Federal regulations and any conditions or restrictions imposed by the reviewing IRB. The Sponsor will incorporate monitoring of the study with attention to verification of clinical requirements, adherence to Study Protocol, and compliance with applicable government and institutional regulations. If necessary, the Investigator will provide the monitor access to all necessary records to ensure the integrity of the data.

The Investigator(s) and institution(s) will permit monitoring, audits, IRB review, and regulatory inspections and provide direct access to source documents. Study sites may be monitored on a periodic basis throughout the course of the study.

Study monitors

Sponsor designated Clinical Research Specialists or appropriately trained staff will complete any monitoring for this study.

Site Visits

Site initiation visits may be made by the Monitor to review the Study Protocol and documentation requirements with the Investigator and clinic support staff involved with the study. The Sponsor will ensure that all researchers involved in the project have adequate training.

Ongoing monitoring visits of the study centers may be conducted to compare the data recorded in the eCRFs with the information contained in the original source documents (source data verification). Monitoring, when conducted, will include at a minimum the following items:

- Patient identification number
- Patient signed informed consent obtained

- Medical record of Adverse Events

Management of the study sites will be predominantly achieved by communications via letter, fax, electronic mail and/or telephone.

Site closure activities will be conducted after all patients have been enrolled and data collection has been completed if deemed necessary. Site closure may be conducted by site visits or by telephone as determined by the Sponsor.

Monitoring Reports

Reports of any monitoring visits will be prepared and maintained by the Sponsor which include:

- The date of the visit
- The name of the individual who conducted the visit
- The name and address of the Investigator visited
- Statement of the findings, conclusions and actions taken to correct any deficiencies noted during the visit

Study Discontinuation or Termination

Investigational Site Termination

The Sponsor reserves the right to terminate a research site for any of the following reasons:

1. Failure to secure Informed Consent from a patient enrolled into the study
2. Repeated Study Protocol violations
3. Repeated failure to complete Electronic Case Record Forms on a timely basis
4. Failure to report Adverse Events on a timely basis
5. The Investigator requests discontinuation

Premature Discontinuation of the study

If the study is prematurely terminated or suspended, the Sponsor or designate will promptly inform the Investigators/institutions of the termination or suspension and the reason(s) for the termination or suspension. The IRB will be informed promptly, if applicable, and provided with a detailed written explanation for the termination or suspension by the Sponsor or by the Investigator/institution, as specified by the applicable regulatory requirement(s).

Ethical Statement

Institutional Review Board (IRB)

Prior to initiation of the study, the Study Protocol, patient informed consent, and any other relevant study documentation will be submitted to a central IRB. For each participating center, IRB approval must be obtained, either through the central or local IRB, and forwarded to the Sponsor before data collection at the site can be initiated. Furthermore, any necessary extension or renewal of the IRB approval must be obtained and forwarded to the Sponsor. In particular, change(s) to any aspect of

the study, such as modification(s) of the Study Protocol, the written informed consent form, or any written information provided to patients must be approved, in writing, by the IRB.

The Investigator at the study site will report promptly to the IRB any new information that may adversely affect the conduct of the study. Similarly, the Investigator will submit written summaries of the study status to the IRB annually, or more frequently, if requested by the IRB. Upon completion of the study, the Investigator will provide the IRB with a brief report of the outcome of the study, if required.

Ethical conduct of the study

The study is to be conducted according to the approved Study Protocol. The Guidelines of the World Medical Association Declaration of Helsinki and the HIPAA Privacy Rule will be strictly followed as well as any other applicable rules and regulations.

Disclosure of data and publication policy

Disclosure of data

By signing the final Study Protocol, every participating Investigator agrees to keep all information and results concerning the study confidential for as long as the data remain unpublished. The confidentiality obligation applies to all personnel involved at the investigational site. Publication of study results requires mutual agreement between the Investigator(s) and the Sponsor.

Sponsor may disclose data derived from the study to other Investigators and domestic or foreign regulatory authorities.

Publication policy

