The study is planned to be divided into four periods as illustrated in Figure 4. The only clinical measures to occur from the beginning of Period I are the StepWatch, Patient Journal, and Socket Comfort Score. After enrollment, the subject will spend 8 weeks (+/-2 weeks) using their own energy storage and return foot. Informed consent, demographic information, general health information, and adverse events will be collected during this period. After enrollment, the subject will be randomized to Revo, Taleo (if a transfemoral amputee), or the Proflex XC (if a transtibial amputee).

Period II – Period IV

Baseline measures are taken just prior to Period II. After the first 8 week follow up, the subject will crossover to the second comparator. After the second 8 week follow up, the subject will crossover to control. During Period IV, assessments will be repeated as in baseline. Table 2 summarizes the assessments and order of events.

[figure not shown]

Figure 4 Study Periods and Visits

Table 2 Assessments by Period and Study Visit

Period I (Control)			Period II (Revo/ Comparative)	Period III (Revo/ Comparative)	Period IV (Control)
	Visit 1	Visit 2	Visit 3	Visit 4	Visit 5
Measurement	Enrollment	Baseline 8 ± 2 weeks	Period II Follow up 8 ± 2 weeks	Period III Follow up 8 ± 2 weeks	Period IV Follow up 8 ± 2 weeks
Demographics / General Health	X				
SCS	X	X	X	X	X
ABC (extended)		X	X	X	X
PLUS-M		X	X	X	X
PROMIS-F (7a)		X	X	X	X
TAPES-FUN + TAPES-AR		X	X	X	X
EQ-5D-5L		X	X	X	X
6 Minute Walk Test (incl. BORG RPE and continuous HR)		X	X	X	X
Foot Preference Questionnaire					X
Patient Journal (incl. Pain Interference)	X	X	X	X	X
Step Count*	X	X	X	X	X
Adverse Events	X	X	X	X	X
Fitting with prosthetic foot for subsequent Period		X	X	X	

* Subject is fitted with StepWatch at previous visit so that the data may be collected prior to the following visit, this process starts at enrollment

Objectives

Safety

Safety Objectives

1. To characterize all device-related adverse events, stumbles, and falls experienced by subjects in the study by frequency and severity.

Effectiveness

Primary Efficacy Objectives

1. To characterize perception of mobility as measured by the PLUS-M while wearing the Revo-M compared to the everyday feet.
2. To characterize the level of activity restrictions as measured by the Trinity Amputation and Prosthesis Experience Scales Activity Restrictions subscale (TAPES-AR) while wearing the Revo-M compared to the everyday feet.

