The Investigator will inform the patient of the aims and methods of the study. The patient must be given every opportunity to clarify any points he/she does not understand and if necessary, ask for more information. At the end of the interview the patient may be given time to reflect if this is required, or more time for discussion with family, caregivers or their own General Practitioner. Patients and/or legal guardians will be required to sign and date the informed consent form. After completion, informed consent forms will be kept and archived by the Investigator in the Study File, and a copy given to the patient.

Prior to the beginning of the study, the Investigator will provide the Sponsor with a copy of the sample informed consent form approved by the IRB and evidence that the IRB has approved the study. The Sponsor must approve any changes to the informed consent form template.

It should be emphasized that the patient is at liberty to withdraw their consent to participate at any time, without penalty, loss of benefits or normal medical care to which the patient is otherwise entitled. Patients who refuse to give, or withdraw written informed consent will not be included or continue in this study.

Data collection

Data will be collected and entered by the Investigator in the form of electronic Case Report Forms (eCRFs) into an Electronic Data Capture (EDC) system by means of prospective data collection.

The following eCRFs are planned to be used for prospective data collection at participating sites:

1. Enrollment
2. Baseline
3. Follow-up
4. Patient Journal

5. Adverse Event
6. Study Termination

Enrollment

After a patient has signed the written Informed Consent Form and meets the inclusion-exclusion criteria, the patient will be considered enrolled in the study. At this point, demographic data, medical history (including fall history) will be collected.

Alignment Assessment

All subjects will undergo an assessment of alignment by the CPO with their current ESR foot. Minor changes to the alignment may be done if the CPO deems it necessary.

Baseline Testing

Baseline testing with the patient's current ESR foot will be conducted at the end of Period I and will include four questionnaires, the PLUS-M, EQ-5D-5L, PROMIS Pain Interference short form, and the extended Activity-specific Balance Confidence Scale. One performance measure will be conducted, the six-minute walk test (see Clinical Tests & Measures for test descriptions).

Randomization

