The fittings during Period II and Period III are determined at random and according to amputation level. Subjects will be randomized to start with either the Revo (regardless of amputation level) or the comparative foot: Taleo if TF or KD, Proflex XC if TT. After completing Period II with the assigned foot, subjects will cross over to be fit with either the Revo, if starting with the comparative foot or the comparative foot if starting with the Revo.

Fitting process for the Revo-M investigational foot

The Revo prosthetic foot has several components which have different mechanical characteristics to allow the foot to be tailored to the patient. Subjects will complete several walking trials to determine the optimal configuration.

Fitting process for the comparative feet: Taleo and ProFlex XC

The Taleo is customizable with heel wedges that come in three different stiffnesses (soft, medium and hard). The CPO may give the subjects the opportunity to try each wedge to determine which is best.

ProFlex XC does not have any customizable components, so no configuration process is required.

Home-use Periods

Subjects will have four home-use periods during the study approximately 8 weeks in duration as shown in Figure 4 above. Prior to each home-use period, subjects will be fitted with the assigned foot and be given a Patient Journal and a StepWatch activity monitor. The Patient Journals will be completed weekly for the duration of the home-use period. The StepWatch will be worn for approximately one month and then mailed back to the clinical site. At the end of the home-use period, subjects will return to the site for a follow-up visit for assessments (see Clinical Tests & Measures for test descriptions).

Clinical Tests & Measures

Data collection for the following clinical functional assessments will be collected on eCRFs. Several questionnaires and two performance based measures will be used in the study.

For an overview of the assessments required by visit, see Table 2.

Activity monitoring (daily step counts)

The StepWatch will be used for activity monitoring to collect daily step counts during the first month of each home-use period.

Six-minute walk test (6minWT)

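### The Baseline Testing text lists four questionnaires and omits TAPES-AR (one of two primary endpoints), TAPES-FUN and PROMIS Fatigue 7a, contradicting Table 2, which requires all three at Visit 2

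*Combined protocol and SAP*

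**What the plan says.** Under Study Procedures, the Baseline Testing paragraph states that testing on the current foot at the end of Period I "will include four questionnaires, the PLUS-M, EQ-5D-5L, PROMIS Pain Interference short form, and the extended Activity-specific Balance Confidence Scale". It adds the six-minute walk test and closes with a pointer: "see Clinical Tests & Measures for test descriptions".

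Table 2 (Assessments by Period and Study Visit) has a row labelled "TAPES-FUN + TAPES-AR" and a row for PROMIS Fatigue 7a. Both are marked at Visit 2, the baseline visit, and at Visits 3 to 5.

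Two sentences describe the role of the table. The Study Summary says "Table 2 summarizes the assessments and order of events". Clinical Tests & Measures says "For an overview of the assessments required by visit, see Table 2".

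Two statements in the statistical part determine what depends on this visit. Under Hypothesis, outcomes after 8 weeks on the Revo-M "will be compared to baseline measures obtained using everyday feet with a 2-sided Wilcoxon matched pairs signed ranks test". Under Data Analysis, "For each variable analyzed, only subjects with valid values will be included in the analysis".

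**The concern.** The Baseline Testing list is counted, so it reads as complete and not as a set of examples. One of the instruments it leaves out measures a primary endpoint. No sentence says which text governs if the paragraph and the table differ.

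The primary test is paired, so a subject without a baseline TAPES-AR contributes nothing to it, whatever is collected later on the Revo-M. Table 2 also places the fitting of the next foot at Visit 2. Once the subject has left on the study foot, the Period I everyday-foot measurement cannot be repeated. The same holds for TAPES-FUN in the secondary family.

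The text on the home-use follow-up visits gives no closed list of this kind. A site could therefore collect TAPES on the Revo-M and miss it at baseline, which is the visit that the paired test most needs.

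**Working it through.** **1. The two texts for Visit 2**

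| Instrument | Role in the plan | Baseline Testing paragraph | Table 2, Visit 2 |
|---|---|---|---|
| PLUS-M | primary #1 | listed | marked |
| TAPES-AR | primary #2 | absent | marked |
| Extended ABC | secondary #2 | listed | marked |
| TAPES-FUN | secondary #3 | absent | marked |
| EQ-5D-5L | exploratory | listed | marked |
| PROMIS Fatigue 7a | exploratory | absent | marked |
| PROMIS Pain Interference | exploratory | listed | marked, within the Patient Journal |

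Three instruments are missing from the paragraph. Both texts are current.

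**2. The plan's own sample size**

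The Sample Size section gives, for TAPES-AR, a difference of 0.2, an SD of 0.3, alpha 0.05, 80% power and 21 subjects. The analysis is two-sided.

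- Effect size: 0.2 / 0.3 = 0.667.
- Method: paired noncentral t, with n multiplied by the signed-rank efficiency 3/π = 0.955.
- Effective n: m = 0.955 × n. Noncentrality: 0.667 × √m. Degrees of freedom: m − 1.
- n = 20: m = 19.1, power 78.7%.
- n = 21: m = 20.05, noncentrality 2.99, critical t 2.09, power 80.8%.

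The smallest n reaching 80% is 21, as stated. The same method gives 22 for PLUS-M (5 points, SD 7.7), also as stated.

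**3. Margin for lost pairs**

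With the minimum of 24 subjects, 24 − 21 = 3 pairs can be lost before the number falls below 21. With the maximum of 30, 30 − 21 = 9 can be lost.

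**4. Illustration**

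The Clinical Study Summary allows up to 5 sites. The documents give no site sizes and no rate at which sites would follow the paragraph. I assume 4 or 5 equal sites, one of them affected, and no other losses.

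| Subjects | Affected | Pairs left | Power at two-sided 0.05 |
|---|---|---|---|
| 24 | none | 24 | 86% |
| 24 | 1 of 5 sites | 24 × 4/5 = 19.2, about 19 | 76% |
| 24 | 1 of 4 sites | 24 × 3/4 = 18 | 74% |
| 30 | 1 of 5 sites | 30 × 4/5 = 24 | 86% |
| 30 | 1 of 4 sites | 30 × 3/4 = 22.5, so 22 to 23 | 83% to 85% |

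Simulation of the signed-rank test on normal differences (20,000 runs) agrees: 0.87 at 24 pairs, 0.80 at 21, 0.77 at 19 and 0.74 at 18. All of these figures use alpha 0.05 for TAPES-AR alone, as the plan's sample-size calculation does.

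**The case against.** The strongest reply is that the protocol does schedule the measurement. Table 2 marks TAPES at Visit 2, and two sentences present the table as the schedule of assessments. The Baseline Testing paragraph itself refers to Clinical Tests & Measures, which describes TAPES and points to Table 2. Sites are also trained on the data collection protocol and the eCRFs before they start. This stands. A reader might infer from the paragraph that no baseline TAPES-AR is planned, or that primary endpoint #2 cannot be tested; the documents do not support that. It would take every site, or the eCRF itself, to follow the paragraph against the table.

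The reply does not remove the contradiction. The pointer in the paragraph offers descriptions of tests, and someone who has read a list of four has little reason to look for more.

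Three further limits are fair:

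- **eCRF content.** The Data collection section plans a separate Baseline form, but the documents do not show what is on it. Nothing indicates that it was built from the paragraph.
- **Visit 5.** TAPES is collected again on the everyday foot at the end of Period IV, so a Revo-M minus everyday-foot difference could still be formed. The plan uses the Period IV comparison only under Exploratory Efficacy Endpoints; it does not replace the baseline in the primary test.
- **Margin.** The Sample Size section raises the maximum to 30 to cover early exit and missing data. At 30, losing one site would leave power above 80%. That margin is also meant to cover ordinary dropout.

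A reader might also treat the two primary endpoints as co-primary, so that losing one would sink the trial. Under the Hochberg procedure either can succeed alone, and PLUS-M would be unaffected as a measurement.

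**Conclusion.** The point holds as an internal contradiction in operational text that bears on a primary endpoint. The mismatch between the Baseline Testing paragraph and Table 2 is certain. Loss of data is conditional: it occurs only where a site or the Baseline eCRF follows the paragraph, and nothing in the documents says how likely that is.

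Where it does occur, each affected subject drops out of the planned baseline comparison for TAPES-AR and for TAPES-FUN. If one of 4 to 5 equal sites is affected, TAPES-AR power is 74% to 76% with 24 subjects and 83% to 86% with 30. Whether it falls below the planned 80% therefore depends on enrolment. These figures rest on the assumed site split, the plan's own difference and SD, and no other missing data. They show the scale of the risk and do not predict a loss. The correction should be made because it is very cheap and a missed baseline cannot be recovered.

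**What to change.** In Baseline Testing, replace the list of four questionnaires with a statement that all assessments marked for Visit 2 in Table 2 are to be done, including TAPES-AR, TAPES-FUN and PROMIS Fatigue 7a. A reference to the table is safer than a second hand-copied list, which could again leave out items such as step count and adverse events, both marked at that visit.

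Confirm that the Baseline eCRF contains these three instruments, and that they are completed before the subject is fitted with the first study foot.

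The cost is one sentence and one check of the form. Table 2 already schedules the assessments, so no procedure, visit or burden on subjects is added. The 21 subjects required for TAPES-AR and the minimum of 24 stay as they are.
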